2.0 OBJECTIVES AND ENDPOINTS

2.1 Objectives

The objectives of this study are:

- To characterize the pharmacokinetics/pharmacodynamics (PK/PD) of rifaximin ER and DER in subjects with sickle cell disease (SCD)
- To assess the safety and tolerability of rifaximin ER and DER

2.2 Endpoints

2.2.1 Pharmacokinetics and Pharmacodynamics

Full rifaximin and 25-desacetyl rifaximin plasma PK profiles following administration on Days 1 and 29 and C_{max} and C_{trough} on Days 8, 15, and 29 will be evaluated.

Blood samples for PK analysis will be collected at the following timepoints:

- Day 1 and Day 29: pre-dose, 0.5, 1, 1.5, 2, 3, 4, 5, and 8-hours post-dose.
- Day 8 and Day 15: pre-dose and 0.5, 1, and 2-hours post-dose.
- Day 29: pre-dose, 0.5, 1, 1.5, 2, 3, 4, 5, and 8-hours post-final dose
- Day 30: 24 and 30 hours post-final dose
- Day 31: 48 hours post-final dose
- Day 32: 72 hours post-final dose
- During medical facility visit for VOC with estimated time of last dose, when possible.

PD biomarkers (ANC, CANs, serum CD62L, hsCRP, the gut permeability biomarkers serum iFABP and LPS, and the gut bacteria biomarker urine 3-indoxyl sulfate) will be collected at the following timepoints:

- Day 1: pre-dose
- Day 8, Day 15, and Day 29: during each visit – pre dose
- Day 31
- Day 43
- During medical facility visit for VOC, when possible.

2.2.2 Safety

Safety will be assessed throughout the duration of the study by collection of adverse events (AEs), vital signs (systolic and diastolic blood pressure, heart rate, oral body temperature, and oxygen saturation), clinical safety laboratory tests (chemistry, coagulation, hematology, urinalysis, and high sensitivity C-reactive protein (hsCRP), physical examinations, and electrocardiograms (ECGs). The safety endpoints are the following:

- Incidence of treatment-emergent adverse events (TEAEs) and serious adverse events (SAEs)
- Clinically significant changes from Baseline in clinical laboratory results
- Changes from Baseline in vital signs

2.2.3 Exploratory Assessments

Information on any potential VOCs experienced during the study will be collected as follows:

- Dates and duration of each episode. A VOC is defined as:
 - The occurrence of appropriate symptoms consistent with a painful crisis, acute chest syndrome (ACS), or priapism, and
 - Requires visit to a medical facility, and
 - Receipt of either a parenteral or oral opioid or NSAID analgesia.
- Categorization of VOCs. Subcategories will consist of:
 - Uncomplicated pain crisis, defined as a painful crisis that is NOT classified as an acute chest syndrome, hepatic sequestration, splenic sequestration, or priapism.
 - Acute Chest Syndrome (ACS), defined as a finding of a new pulmonary infiltrate involving at least one complete lung segment that was consistent with alveolar consolidation, but excluding atelectasis (as indicated by chest X-ray). Must also present with at least one of the following signs or symptoms: patient-reported chest pain, body temperature of more than 38.5 °C, tachypnea, wheezing, or cough.
 - Hepatic sequestration, defined as findings of right upper quadrant pain, an enlarged liver, and an acute decrease in hemoglobin concentration.
 - Splenic sequestration, defined as findings of left upper quadrant pain, an enlarged spleen, and an acute decrease in hemoglobin concentration.
 - Priapism, defined as having a sustained penile erection requiring a visit to a medical facility.

- Intravenous opioid analgesia (IOA) and oral opioid use during VOCs, including date/time of each start and stop of treatment, dose, drug, inpatient/outpatient setting, and date/time of readiness-to-discharge.

3.0 INVESTIGATIONAL PLAN

3.1 Overview of Study Design

Study RBSC2161 is a Phase 2a, randomized, double-blind, placebo-controlled, multicenter study to evaluate the pharmacokinetics (PK), pharmacodynamics (PD) safety and tolerability of rifaximin ER and DER in subjects with SCD. Exploratory assessments of the effect of rifaximin ER and DER on the incidence of VOCs will also be explored.

Approximately 60 subjects who successfully complete the Screening Period will enter the Treatment Period and will be randomized to one of six treatment groups. Approximately 20 study centers are expected to participate in the study.

Objectives and endpoints for the study are provided in [Section 2](#). Assessments of PK/PD and safety, and documentation of VOCs ([Appendix 1](#) and [Section 7.3](#)) will be performed during clinic visits at Baseline (Day 1), Day 8, Day 15, and Day 29 (End of Treatment/Early Termination). All subjects will also complete an End of Study (EOS) Visit 2 weeks later (Day 43; End of Study) for final assessments. Assessments will also be conducted when a subject visits a healthcare facility for treatment of a VOC. If a subject prematurely discontinues treatment, every attempt will be made to obtain EOT and EOS assessments and subjects should be followed until the end of the 43-day trial.

Before study subjects can be screened, the laboratory where the CANs assessment will be performed shall undergo a qualification run. This is to ensure that the flow cytometry assessment for CANs can be performed at the local site as outlined in the Laboratory Manual. The qualification run will be performed with blood from healthy, adult, non-pregnant, and capable volunteers of general good health (and non-sickle cell disease subjects). Approximately 25 healthy volunteers (one per site, or per local lab) is expected to participate. Healthy volunteers will visit the study center once for this assessment (single blood draw) and it should take no more than 30 minutes to complete the testing.

3.2 Treatment Assignment/Randomization

Subjects who meet the eligibility criteria and have given written informed consent will be randomized in a 2:2:1:2:2:1 allocation to one of 6 treatment groups. Approximately 12 subjects will be randomized to each active rifaximin treatment and approximately 6 subjects to each placebo group. The treatment groups will be run in parallel.

- Group 1: 40 mg rifaximin ER, BID
- Group 2: 40 mg rifaximin DER, BID
- Group 3: Placebo for 40 mg rifaximin, BID

- Group 4: 80 mg rifaximin ER, BID
- Group 5: 80 mg rifaximin DER, BID
- Group 6: Placebo for 80 mg rifaximin, BID

3.3 Procedures for Breaking the Blind

Subjects, study staff, and the Sponsor will be aware of the dose groups (2 x 20 mg capsules BID or 4 x 20 mg capsules BID) but will be blinded to active or placebo. Only in the case of an emergency, when knowledge of the study drug is essential for the clinical management or welfare of the subject, will the Investigator be allowed to unblind a subject's treatment assignment. To discuss breaking of the blind, the Investigator should contact the Medical Monitor. The Investigator will unblind via an Interactive Response Technology system.

If the Investigator breaks the blind for an individual subject, the reason must be in the subject's source documents and the subject will be removed from the study.

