4.5 Premature Subject Discontinuation

All subjects are free to withdraw from participating in this study at any time for any reason, specified or unspecified, and without prejudice. No constraints will be placed on ordinary subject management, and subjects, when appropriate, will be placed on other conventional therapy upon request or whenever clinically necessary as determined by their physician.

Withdrawal of the subject from treatment with study drug or from the study will be considered, in consultation with the Sponsor, or designee, for any of the following reasons:

- The subject withdraws consent.
- The subject experiences an intolerable AE or SAE.
- The subject experiences CDAD
- The subject enrolls into another interventional clinical study in which an investigational treatment or approved therapy for investigational use is administered.
- The subject becomes pregnant. Study treatment must be discontinued immediately. Report the pregnancy according to the instructions in [Section 7.10](#).
- The subject is unwilling or unable to comply with the protocol.
- At the discretion of the Investigator or Sponsor.

- Investigator decision that it is not in the best medical interest of the subject to continue participation in the investigation.

Prior to discontinuing a subject, every effort should be made to obtain as much follow-up data as possible. Withdrawn or discontinued subjects will undergo early termination procedures per the scheduled assessments for the Early Termination (ET) Visit. AEs will be followed as described in [Section 7.8](#). Subject withdrawals will be documented clearly on the source documents and applicable eCRFs.

Notification of subject withdrawals will be made to the Sponsor, or designee.

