7.5 Documenting AEs and SAEs

All AEs that occur after the subject has signed the ICF through 28 days after last dose of study medication, regardless of causality or seriousness, will be assessed and recorded in the subject's

source documents and in the eCRF. If a subject is withdrawn during treatment, they must be followed for 28 days after the last dose as well. In addition, SAEs must be documented on the paper SAE Report Form.

The Investigator should attempt to establish a diagnosis for the event based on signs, symptoms, and/or other clinical information. In such cases, the diagnosis should be documented as the AE or SAE and not the individual signs/symptoms. When this is not possible, the AE should be documented in terms of signs and/or symptoms observed by the Investigator or reported by the subject at each study visit. Each AE which appears to be independent of any prior event will be reported separately.

For clinically significant abnormal laboratory findings or other abnormal assessments meeting the definition of an AE or SAE, a diagnosis, if known (or clinical signs and symptoms if a diagnosis is unknown), should be recorded by the Investigator. If a diagnosis is unknown and clinical signs and symptoms are not present, then the abnormal finding should be recorded. When documenting as an SAE on the SAE Report Form, relevant laboratory (including the reference range and units) or copies of the laboratory report (with reference ranges and units) should be sent with the SAE Report Form.

The SAE Report Form should be completed as thoroughly as possible and signed by the Investigator or his/her designee before transmittal to the Sponsor/designee. Investigators should not wait to receive additional information to fully document the event before notifying the Sponsor of an SAE. It is very important that the Investigator (or designee) provide his/her assessment of causality to study product at the time of initial SAE reporting.

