7.8 Follow-up of AEs and SAEs

All AEs, regardless of seriousness, must be followed until resolution, until the condition stabilizes, until the event is otherwise explained, or until the subject is lost to follow-up. The Investigator is responsible for ensuring that follow-up includes any supplemental investigations as may be indicated to elucidate as completely as practical the nature and/or causality of the AE. This may include additional laboratory tests or investigations, histopathological examinations, relevant hospital records (i.e., discharge summary), or consultation with other health care professionals.

Salix may request that the Investigator perform or arrange for the conduct of supplemental measurements and/or evaluations. If a subject dies during participation in the study or during follow-up period, the Sponsor/designee should be provided with a copy of any postmortem findings, including histopathology.

If cause of death is not available within the 24-hour reporting period, “death” must be reported as SAE term to meet timelines and the cause of death actively queried and submitted as a follow-up report.

When additional SAE information becomes available, it should be recorded on a new SAE Report Form and should be labeled as a “Follow-up Report”. The original SAE Report Form should not be altered. All completed SAE Report Forms must be signed and dated by the Investigator or designee. By signing the SAE Report Form, the Investigator or designee attests to the accuracy and completeness of the data and that he/she has reviewed and approved the report being submitted. The investigational sites IRB/EC must be notified about SAEs in accordance with the requirements of the governing IRB/EC.

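### Section 3.3 ends study participation after a code break, which does not fit the follow-up in 3.1 and 7.5 and leaves later PD, VOC and Day 43 data unprotected

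*Combined protocol and SAP*

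**What the plan says.** - **Section 3.3** allows unblinding "Only in the case of an emergency, when knowledge of the study drug is essential for the clinical management or welfare of the subject". If the Investigator breaks the blind, the reason goes into the source documents and "the subject will be removed from the study". Nothing is said about later visits or data, and no other section is referred to.
- **Section 3.1** sets an EOS visit at Day 43 for all subjects. For those who stop treatment it adds: "If a subject prematurely discontinues treatment, every attempt will be made to obtain EOT and EOS assessments". On how long observation lasts, the same section states that "subjects should be followed until the end of the 43-day trial".
- **Section 7.5** says: "If a subject is withdrawn during treatment, they must be followed for 28 days after the last dose as well".
- **Section 4.5** distinguishes withdrawal from study drug from withdrawal from the study, and treats either as a matter to weigh with the Sponsor. A code break is not among its listed reasons. It also says: "Withdrawn or discontinued subjects will undergo early termination procedures per the scheduled assessments for the Early Termination (ET) Visit". Before a subject is discontinued, "every effort should be made to obtain as much follow-up data as possible".
- **Section 7.8** says: "All AEs, regardless of seriousness, must be followed until resolution", or until the event stabilises, is explained, or the subject is lost to follow-up.
- **Section 7.3** keeps VOCs, including acute chest syndrome, out of AE and SAE reporting and has them recorded on their own eCRF page to Day 43.
- **Section 8.4.13** analyses available data only. **Section 4.6** allows withdrawn subjects to be replaced. **Section 8.3** keeps every dosed subject in the Safety Population.

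**The concern.** A subject whose code is broken comes under two sets of instructions. Section 3.3 takes the subject out of the study automatically. Sections 3.1 and 7.5 describe observation that goes on after treatment has stopped. A site that follows 3.3 to the letter could close the subject's record after the early termination visit.

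The number of subjects matters less than how they are selected. The blind may be broken only in an emergency, so any data that stop at that point stop for a reason that may be connected with outcome. Safety and tolerability is one of the two study objectives, PD is part of the other, and VOCs are the exploratory clinical outcome. Nothing is imputed, so later-visit summaries would simply omit these subjects.

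**Working it through.** **1. Do the instructions fit together?**

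| Section | Trigger | Instruction | Strength |
|---|---|---|---|
| 3.3 | Blind broken | Out of the study | Unconditional |
| 3.1 | Treatment stopped early | EOT and EOS assessments; follow to Day 43 | An aim, not an absolute duty |
| 7.5 | Withdrawn during treatment | Follow for 28 days after last dose | Mandatory |
| 4.5 | Withdrawn or discontinued | ET procedures | Mandatory |

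Sections 4.5 and 7.5 can be read as saying what happens after removal, so they can coexist with 3.3. Section 3.1 cannot easily do so, because it expects a subject who is off treatment still to be in the study at Day 43.

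**2. What happens if 3.3 is followed literally?** Two other provisions help the record to close. Under 6.1.10, a visit at which a subject is discontinued counts as Visit 9. That is the Day 43 EOS visit, although 6.1.10 labels it EOT; the EOT/ET visit is Visit 5. An emergency visit could therefore stand in for Day 43. Section 7.4.2 does not oblige sites to look for SAEs once a subject's participation is over, and a removed subject can be read as falling under it.

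**3. Which data are protected?**

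| Data | Protected by | Gap under a literal 3.3 |
|---|---|---|
| Data before removal | 8.3 | None |
| The emergency, if an AE or SAE | 7.5, 7.8 | None |
| ET assessments | 4.5, 6.1.10 | None |
| New AEs to last dose + 28 days | 7.5 | Only if the site applies 7.4.2 instead |
| Later VOCs | 7.3 only | Open: outside AE follow-up |
| Later PD samples, Day 43 assessments | 3.1 only | Open |
| Later PK samples | None | Open; dose-timed samples matter only if dosing continues |

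**4. Calendar.** With the last dose on Day L, 7.5 runs to Day L + 28, and 3.1 runs to Day 43.

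| Last dose (L) | 7.5 ends (L + 28) | Relative to Day 43 | Days from last dose to Day 43 |
|---|---|---|---|
| Day 1 | Day 29 | 14 days short | 42 |
| Day 8 | Day 36 | 7 days short | 35 |
| Day 15 | Day 43 | Equal | 28 |
| Day 22 | Day 50 | 7 days beyond | 21 |
| Day 29 | Day 57 | 14 days beyond | 14 |

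The two periods agree only for a last dose on Day 15. For a subject who completes treatment on Day 29, the 28-day window ends two weeks after the last planned visit. That mismatch exists with or without a code break. Where 7.5 is honoured, AE observation falls short of Day 43 by at most 14 days. The last column is the ceiling for VOC observation.

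**5. Size.** Each active group has 60 × 2/10 = 12 subjects, and the combined placebo group has 6 + 6 = 12.
- One subject missing from a later visit is 1/12 = 8.3% of a group. At the same SD, the standard error of a mean rises by √(12/11) = 1.04.
- Two subjects are 2/12 = 16.7%, with a factor of √(12/10) = 1.10.
- The documents give no unblinding rate. For an assumed rate p per subject, the chance of at least one code break in 60 is 1 − (1 − p)^60.

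| Assumed p | Expected (60p) | Chance of at least one |
|---|---|---|
| 0.5% | 0.3 | 26% |
| 1% | 0.6 | 45% |
| 2% | 1.2 | 70% |
| 5% | 3.0 | 95% |

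**The case against.** The best defence is that 3.3 is silent about follow-up and does not forbid it, and that other sections supply what it leaves out. Section 7.5 is written for withdrawn subjects, and a subject removed during treatment is one. Section 4.5 orders the ET procedures, 6.1.10 asks for EOT assessments when a subject is discontinued at an unscheduled visit, 7.8 follows every AE, and 7.1.2 adds a PK sample after an SAE. Section 3.1 is triggered by stopping treatment and is worded as an aim, so it is not a strict requirement that 3.3 breaks. Taking an unblinded subject out of a double-blind study is also a choice open to a sponsor, and the analyses are descriptive.

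Most of this stands for adverse events, and for that reason a reader should not infer that the safety record of the emergency is lost. The emergency comes before the code break; if it is an AE or SAE it is recorded and followed, and it stays in the incidence tables. A VOC emergency is recorded on its own eCRF page.

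The defence does not reach the rest. Section 7.8 follows events that already exist and does not provide for finding new ones. Sections 7.5 and 7.8 concern AEs, and 7.3 puts VOCs outside them. The effort in 4.5 to gather data applies before discontinuation. No section says that PD sampling and the Day 43 assessments continue for a subject whom 3.3 has removed.

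**Conclusion.** The point holds in a limited form. Section 3.3 does not separate treatment status from study status and does not fit with 3.1 and 7.5. Read literally, it allows a site to stop the remaining scheduled PK/PD samples, the Day 43 assessments and later VOC capture in subjects selected by an emergency.

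Three stronger conclusions might be drawn, and the documents support none of them:
- **That later summaries would look too favourable.** Missingness related to outcome is plausible, but nothing shows that these subjects would have had worse later values. The direction of any bias is unknown.
- **That about six weeks of safety observation disappear.** The 42-day ceiling applies to VOC observation after a last dose on Day 1. For AEs under 7.5 the shortfall against Day 43 is at most 14 days, and it is nil from a last dose on Day 15 onward.
- **That 8.3% of a group's safety data is lost.** That figure is a share of subjects at later visits. All data up to and including the ET visit are kept.

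The number affected is probably small, but that rests on an assumed rate. The text should be corrected, although the main PK and safety results do not depend on it.

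**What to change.** Reconcile 3.3 with 3.1, 4.5, 6.1.10, 7.4 and 7.5:
1. In 3.3, state that, whatever the sponsor decides about treatment, a code break does not by itself end study participation. ET, Day 43/EOS, PD, VOC and AE follow-up data continue to be collected as already scheduled unless the subject withdraws consent.
2. Record each code break, with its date and reason, so that it can be listed.
3. Make clear in 7.4 that such a subject is not a former subject for as long as follow-up lasts.
4. Correct 6.1.10, which attaches the EOT label to Visit 9, and say whether a discontinuation visit replaces Day 43.
5. Resolve the 28-day window in 7.5 against the Day 43 last visit, since a last dose on Day 29 takes it to Day 57.

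The core change is about one sentence in 3.3. It adds no visits beyond those already scheduled and leaves the treatment decision with the sponsor. Item 5 needs a separate decision, because keeping the 28 days would mean some form of contact after Day 43.

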4.0 SELECTION AND WITHDRAWAL OF SUBJECTS

4.1 Inclusion Criteria

A subject will be eligible for inclusion in this study if he/she meets all of the following criteria:

1. Subject must have the ability and willingness to sign a written informed consent form.
2. Subject is between the ages of 18 to 70 years old (inclusive) at the time of consent.
3. Subject has SCD of any genotype (HbSS, HbSC, HbS β-thalassemia). If the subject's genotype has not been previously documented, genotyping will be performed during Screening using high-performance liquid chromatography (HPLC)/electrophoresis.
4. Subject must have experienced at least 2 VOCs within the 12 months prior to Screening.
A VOC is defined as:
 - a. The occurrence of appropriate symptoms consistent with a painful crisis, acute chest syndrome (ACS), or priapism, and
 - b. Requires a visit to a medical facility and/or healthcare professional, and
 - c. Receipt of either a parenteral or oral opioid or NSAID analgesia.
5. If subject is receiving hydroxyurea (HU)/hydroxycarbamide (HC), subject must have been receiving the treatment for at least 6 months prior to Screening and must agree to maintain the same dose and schedule for the duration of the study.
6. Subjects must have laboratory values at Screening within the following ranges:
 - Absolute Neutrophil Count $\geq 1.0 \times 10^9/L$
 - Platelets $\geq 75 \times 10^9/L$
 - Hemoglobin (Hgb) $\geq 6.0 \text{ g/dL}$
 - Glomerular filtration rate (GFR) $\geq 45 \text{ mL/min}/1.73 \text{ m}^2$ using the CKD-EPI formula
Total bilirubin $\leq 15 \text{ mg/dL}$
 - Alanine transaminase (ALT) $\leq 3.0 \times \text{ULN}$
 - International Normalized Ratio (INR) ≤ 2.0
7. Eastern Cooperative Oncology Group (ECOG) performance status ≤ 2 .
8. Women of child-bearing potential, defined as all women physiologically capable of becoming pregnant, must have a negative serum pregnancy test at Screening and agree to use standard prevention methods for the duration of the study.

